STUDY PROTOCOL

Saline vs. Lactated Ringers for Emergency Department IV Fluid Resuscitation

NCT03133767

Date Created: 03/15/17

Date Uploaded: 06/26/18

A. Introduction

A.1. Health Problem Needing Intervention and Impact of Proposed Intervention

Administration of intravascular (IV) fluid is the most common emergency department (ED) procedure¹. IV fluids are integral to increasing effective blood volume and ensuring organ perfusion in patients with volume depletion and dehydration². There are many options of IV fluids providers can use when treating ED patients³. Surveys show physicians do not cite an evidence-based reason for selecting the crystalloid IV fluid used; the decision was likely to be influenced by type and location of practice^{4,5}. A gap exists in the current literature, as there is no evidence for the optimal IV fluid choice for the ED patient requiring IV fluid before discharge.

Normal saline (NS) is commonly used as an IV fluid replacement in ED patients⁶. However, NS has been associated with increased risk of acidosis and acute kidney injury. This study will use a novel approach of a patient-centered outcome in a non-critically ill population to ascertain the optimal IV fluid for patient quality of recovery. The results of this study will inform provider's IV fluid decisions between NS and LR. More importantly, the results of this study will have the power to improve patient's quality of recovery following IV fluid administration and subsequent ED discharge.

B. Background

B.1. Prior Literature and Studies

Common IV fluids used for ED patients are normal saline (NS), a 0.9% sodium chloride solution, and lactated ringer's (LR), another isotonic saline solution³. There is a wealth of literature comparing IV crystalloid solutions, like NS and LR, among others⁷⁻⁹, yet administration of LR and NS by ED providers remains heterogeneous for non-critical ED patients.

NS has been shown to decrease renal arterial blood flow in healthy volunteers¹⁰. Large animal studies support the finding of increased metabolic acidosis and also cite hyperkalemia in subjects receiving NS, when compared to LR¹¹. Increased risk of acidosis is most likely due to high chloride concentration^{3,6}. LR is one of the "low-chloride" crystalloid solutions with a chloride load that is physiologic, or similar to the amount of chloride in human serum. While other low-chloride solutions have not been associated significantly different AKI or mortality than NS¹², observational studies have identified a protective association of LR for acute kidney injury and hospital mortality in critically-ill patients when compared to NS^{13,14}. A recent meta-analysis found an association between high-chloride IV solutions, including NS, and inferior clinical outcomes⁷, but no studies included an outcome of quality of recovery.

This study proposes comparing LR and NS in a non-critically ill population, ED patients receiving fluid before discharge. ED patients presenting with chief complaints likely to be associated with dehydration or volume depletion (nausea, vomiting or emesis, diarrhea, dehydration, heat stroke or exhaustion, and/or abdominal pain) will be included. One previous study has compared LR and NS in patients with severe diarrhea and was stopped for efficacy when LR corrected pH in subjects more quickly than NS¹⁵.

This study will add to the current literature with a comparison of LR to NS on a patient-centered outcome for the most common procedure in emergency department patient populations.

B.2. Rationale for this Study

This is the first study to investigate the patient-centered outcome, quality of recovery, in a trial comparing LR and NS in an ED population stable for discharge. Previous studies indicate there could be an improved patient recovery when patients receive LR solution compared to NS solution as an IV fluid. Quality of recovery will be assessed by patient assessment of Comfort, Emotion, Physical Independence, Patient Support, and Pain.

Results from the proposed study could increase patient recovery at little or no increased cost. Normal saline and lactated ringer's solutions (1000 ml or CC) are similar costs (1.485 and 1.304 Payment Limits, respectively)¹⁶, and both are readily available in most hospital formularies. This study proposes comparing two readily-available, low-cost IV fluids on the basis of patient-reported quality of recovery in patients discharged from the ED.

The study **hypothesis** is emergency department patients receiving lactated ringer's solution will have an improved Quality of Recovery when compared patients receiving normal saline.

C. Study Objectives

C.1. Primary Aim

The primary objective of this study is to compare the quality of recovery in ED patients receiving lactated ringer's and normal saline IV solutions at 24 hours after ED discharge.

C.2. Secondary Aim

The secondary aim of the study is to describe differences in healthcare utilization after ED discharge between subjects in the control NS and intervention LR groups.

D. Study Design

D.1. Overview & Design Summary

This is a single-blind, randomized controlled trial in a single Midwestern emergency department with 60,000 patient visits per year. Enrollment of 156 subjects is planned. Subjects will be randomized to receive a single administration of two liters of either normal saline or lactated ringer's solution. Evaluations will occur at baseline, one day following ED discharge, and seven days following ED discharge.

Potential participants will be screened upon ED registration. Subjects will participate in study for seven days (during ED visit with two remote follow-up contacts at one and seven days). Total duration of the study is expected to be 12 weeks.

D.2. Subject Selection

Subjects will be recruited in the emergency department by two trained research assistants (RAs). Subjects will be recruited beginning in May 2017.

D.2.a. Inclusion Criteria

Patients (1) with a chief complaint of: nausea, vomiting or emesis, diarrhea, abdominal pain, dizziness, weakness, heat stroke or heat exhaustion, dehydration, fatigue, or volume depletion; (2) are deemed by their ED provider to be clinically able to receive two liters of fluid; (3) are being administered fluids by their ED treatment team; and (4) are decided to be likely to be discharged from the ED are eligible for the study.

D.2.a. Exclusion Criteria

Patients without consistent access to a phone with text-messaging capabilities for the following seven days and/or without a primary care physician will be excluded from this study. Patients from the following groups will be excluded: pregnant, prisoners, did not speak English, were undergoing current chemotherapy, signs of jaundice, already received greater than 250 mL of IV fluids, or unable to provide informed consent.

D.2.b. Subject Recruitment Plans, Screening and Consent

Screening will begin as the patient checks in to the ED with the triage nurse and enters a chief complaint. Two RAs will monitor the emergency department electronic patient list in real time to identify patients with eligible chief complaints. The RA will approach the patient's provider to determine if patient meets inclusion criteria (2-4). If the provider determines the patient meets both inclusion criteria, the RA will approach the patient in his/her ED patient room to screen the patient for eligibility based on stated inclusion and exclusion criteria.

If patient meets all inclusion criteria and does not meet any exclusion criteria, the RA will discuss the study with the patient using a standard, IRB-approved script. If the patient is agreeable to participation in the study, written consent will be obtained and proof of research participation will be documented in the patient's electronic medical record.

D.2.c. Randomization Method and Blinding

Randomization of intervention will be 1:1 in randomized, permuted blocks.

Randomization will be performed in SAS (SAS Institute), version 9.4. Blinded allocation ("Drug 1" or "Drug 2") will be placed in sealed opaque envelopes labelled by subject ID before the enrollment period begins. All research team members involved in patient enrollment and outcome assessment (survey administration) will not be involved in this randomization process.

D.3. Intervention

Following randomization, a RA will work with the nursing staff to procure the correct IV solution and administer the solution. Times of initiation and termination of fluid administration and amount of actual fluid administered will be recorded for covariate analysis.

D.3.a. Description

Both intervention and control medications will be delivered intravenously via peripheral venous access at room-temperature. Fluid administration rate will be 1,000 mL/15 minutes by pressure bag method and will be monitored by an RA.

Intervention is 2,000 mL lactated ringer's IV solution (see description below).

"Each 100 mL of Lactated Ringer's Injection, USP contains sodium chloride 600 mg, sodium lactate, anhydrous 310 mg, potassium chloride 30 mg and calcium chloride, dihydrate 20 mg... A liter provides 9 calories (from lactate), sodium (Na⁺), 130 mEq, potassium (K⁺) 4 mEq, calcium (Ca⁺⁺) 3 mEq, chloride (Cl⁻) 109 mEq and lactate [CH₃CH(OH) COO⁻] 28 mEq. The electrolyte content is isotonic (273 mOsmol/liter, calc.) in relation to the extracellular fluid (approx. 280 mOsmol/liter). The pH of the solution is 6.6 (6.0 to 7.5)."¹⁷

Control is 2,000 mL of normal saline (0.9% sodium chloride).

D.3.b. Subject Compliance Monitoring

RAs will record time of initiation and completion of each bag of IV fluid and confirm patient is receiving correct fluid for allocation group. Any crossovers or premature stopping of fluid administration will be documented. Actual amount of fluid (mL) received will be documented.

D.3.c. Data Collection Procedures for Adverse Events

Any adverse event occurring in the ED would be recorded by the RA. Subjects will also be given contact information for a study physician, trained in emergency medicine, and will be instructed to call with concerns or to report any adverse events.

Further, an EM physician, not affiliated with the study, will be presented group data (blinded to treatment allocation) of 28-day patient medical treatment at the enrolling medical facility to assess safety for stopping. This chart review data will be collected by a research team member, blinded to subject group. Subject group ("A" or "B") will be added by study statistician (treatment ["LR" or "NS"] will not be revealed).

D.4. Study Outcome Measurements and Ascertainment

Outcomes will be recorded by trained RAs at time of ascertainment. RA obtaining outcome measurement will be blinded to subject allocation. Data will be entered and stored electronically on a secure server that can be accessed from any location at the enrolling site. Paper surveys will be saved in a locked file cabinet at the enrolling site.

At the time of enrollment, baseline characteristics of subjects will be collected by RAs by in-person interview (pre-intervention QoR-40 score) and from electronic medical record (age, gender). Some baseline characters will be collected at the chart abstraction (ED encounter disposition [discharged from ED/admitted to hospital/admitted to ICU], ED diagnosis type [by organ system]).

D.4.a. Primary Endpoint

The primary outcome of this study will be the post-treatment survey score of the Quality of Recovery-40 (QoR-40, see Attachment H-2) validated survey tool^{18,19}. The survey has been used extensively in the surgery anesthesia literature to measure patient-

reported recovery across five independent domains: Comfort, Emotion, Physical Independence, Patient Support, and Pain. Survey scores range from 40 to 200.

RAs will administer the QoR-40 to subjects initially before any intervention is administered (“pre”). Twenty-four hours following discharge, the RAs will administer the survey again by telephone (“post”). During survey administration, RA will fill-out survey on paper, and it will later be entered into the electronic database. If patient does not answer, two additional phone calls will be made in the 24-48 hours following ED discharge. Time of “post” survey response will be recorded.

D.4.b. Secondary Endpoint

Secondary endpoints are designed to examine differences in healthcare administration between the NS control and LR intervention groups. Secondary endpoints will be assessed at two time points (1) at the 24-hour post-discharge phone call and (2) with a 7-day follow-up text message utilizing a two-way text messaging system.

The following secondary endpoints will be recorded:

- (A) Sought additional healthcare for same complaint,
- (B) Returned to an ED for same complaint,
- (C) Filled an ED prescription from visit of enrollment, and

Each endpoint will be a dichotomous (yes/no) response. No adjudication of “same complaint” will be performed by the research team, as the intention is to capture the patient’s interpretation of healthcare utilization from the illness.

D.4.c. Subgroups

No *a priori* subgroup analyses are planned. Any subgroup analyses performed will be solely for the purpose of hypothesis generation.

E. Statistical Plan

E.1. Sample Size Determination and Power

Sample size calculation was based on the detection of a 10-point difference on the QoR-40 survey scores. A 10-pt difference was selected as the minimum detectable difference maintaining clinical relevance, as supported by previous studies¹⁸⁻²¹. Sample size calculation ($\alpha = 0.05$, $\beta = 0.90$, 20% dropout, difference of 10 points) revealed a need for 156 total subjects.

E.2. Statistical Analysis

Baseline characteristics. Baseline characteristics will be reported with summary statistics as appropriate (mean, SD, median, IQR) and differences in characteristics will be conducted using t-test for continuous variables and chi-square test for categorical variables. If any baseline characteristics have significant differences, those behaviors will be reported in the results section and an adjusted analysis will be performed on primary and secondary variables to assess the impact of the imbalances.

Primary outcome. The primary outcome, pre-post difference in Quality of Recovery-40, will be analyzed using a t-test (if parametric) or Mann Whitney U Test (non-parametric) in an intention-to-treat (ITT) analysis. Due to the nature of emergency department

research, an additional analysis will be done by treatment received and compared to the primary ITT analysis.

Secondary outcome & safety analysis. Secondary outcomes will be reported as a relative risk with 95%CI in an ITT analysis. A safety analysis of selected secondary outcomes (return to ED and seeking additional healthcare for same complaint) will be performed by treatment received.

Covariate analysis. Differences in actual fluid administered and time from intervention to primary outcome will be assessed. If significant, analysis adjusting for covariates of time from intervention to primary outcome, post-QoR-40 administration, and amount of fluid (mL) received will be performed with multivariable linear regression and multivariable logistic regression (primary and secondary outcomes, respectively).

F. Quality Control

F.1. Study Monitoring Plan

Study accrual will be reported weekly by RAs. Study accrual is expected to be about 13 subjects per week. Full research team meetings will occur if study accrual falls below 80% of expected total accrual for any end-of-the-week accrual reports. The purpose of the meeting will be to develop and implement strategies to increase subject accrual. Potential solutions could include utilization of trained ED enrollers currently in the department, additional training and education of ED medical and nursing staff on the study, and recommendations to RAs by current clinicians on increasing visibility and awareness of the study during ED clinical shifts. Concerns will be addressed in a weekly meeting of RAs and investigators at enrollment site.

Safety reporting will occur after enrollment of every 30 subjects (the last group will be 36 subjects). If an adverse event is recorded, the Safety Coordinator will review the event within 24 hours. The local IRB will also be notified.

F.2. Data Review

Data from paper surveys and enrollment forms will be entered into a secure database by the RAs. At the end of enrollment and before analysis, one investigator will perform a 10% audit of the data. Concordance will be measured using a κ statistic. Following audit, the database will be locked for analysis.

G. Study Administration

G.1. Organization and Participating Centers

Enrollment for this single center study will occur at:

Emergency Treatment Center
Department of Emergency Medicine
University of Iowa Hospitals and Clinics
[name]
[name]

[figure not shown]
Investigators, study statistician, research assistants, and safety coordinator are affiliated with the University of Iowa.

H. Attachments

H.1. Procedure Table

Measure	Timeline				
	Baseline (Before Intervention)	During Intervention	Phone call: 24 hours after ED discharge	Text message: 7 days after ED discharge	Chart review: 28 days after ED discharge
Quality of Recovery-40	X		X		
Time and Amount of Fluid Administered		X			
Returned to ED for same complaint			X	X	
Sought additional healthcare for same complaint			X	X	
Filled ED prescription			X	X	
Adverse Event Monitoring		X	X	X	X

H.2. Primary Outcome Survey, “Quality of Recovery-40”¹⁸

I. References

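### Does the plan leave the 24-hour QoR-40 caller unblinded because research assistants also handle the fluid?

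*Combined protocol and SAP*

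**What the plan says.** D.4 sets the requirement for outcome assessment: "RA obtaining outcome measurement will be blinded to subject allocation".

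The protocol also gives RAs three tasks that can reveal the fluid:

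- D.3: "a RA will work with the nursing staff to procure the correct IV solution and administer the solution".
- D.3.a: the infusion runs "by pressure bag method and will be monitored by an RA".
- D.3.b: RAs "confirm patient is receiving correct fluid for allocation group".

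The same job title makes the follow-up call. D.4.a says "Twenty-four hours following discharge, the RAs will administer the survey again by telephone", and "During survey administration, RA will fill-out survey on paper".

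On concealment, D.2.c says the coded allocation "will be placed in sealed opaque envelopes labelled by subject ID before the enrollment period begins". Its one explicit separation of roles is "All research team members involved in patient enrollment and outcome assessment (survey administration) will not be involved in this randomization process".

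D.1 calls the trial single-blind without naming the blinded party, and D.2 has two RAs recruiting.

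**The concern.** One job title covers both the unblinding work and the outcome call. The coded envelopes hide the sequence until assignment. They do not keep an RA blind once that RA has fetched the bag and checked it, since no coded or over-wrapped bags are described. The separation in D.2.c keeps enrolment and survey staff away from randomization only; it does not keep the person who handles the fluid away from the telephone. Read this way, D.4 asserts blinding without a mechanism.

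The primary endpoint is a subjective score from 40 to 200, taken by telephone and written down by the interviewer, and the stated hypothesis favours lactated Ringer's. If prompting or recording differed by arm, the t-test or Mann-Whitney test in E.2 could not separate that from an effect of the fluid. The secondary endpoints are less exposed: they are yes/no answers, and each is asked again at seven days by text message.

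**Working it through.** **1. The sections side by side.** The question is whether D.4 can be obeyed together with D.3, D.3.a, D.3.b and D.4.a.

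- *The RA who handled the fluid calls the same subject.* With unmasked bags that RA knows the fluid, so the call breaches D.4.
- *Another RA, who did not handle that subject's fluid and has not seen the record, makes the call.* D.4 is met, and so are D.3 to D.3.b and D.4.a, because none of them requires one person to do both tasks.
- *Bags are masked in practice.* D.4 can be met whoever calls.

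Two of the three arrangements comply, and the first is ruled out by D.4's own words. The sections do not contradict each other. A requirement is stated, and the means of meeting it is not.

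**2. Is compliance feasible?** F.1 expects about 13 subjects a week. First calls: 13 / 7 = 1.9 a day. D.4.a allows a first call and two more attempts, so the ceiling is 13 × 3 = 39 attempts a week. Two RAs can plausibly share that load. The documents give no shift schedule, so full cover is an assumption.

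**3. Could data entry unblind the caller?** F.2 has RAs enter the surveys and enrolment forms. It does not say that the forms show the fluid, or that they are entered before the call. This route is possible but not shown.

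**4. How large could the effect be if D.4 were not kept?** The plan has no figure for this. An illustration needs three inputs the documents do not give: an SD, the share of unblinded calls, and a shift that differs between arms.

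- Evaluable subjects: 156 × (1 − 0.20) = 124.8, or 62 per arm.
- SD: E.1 gives none. Solving for 90% power at 10 points, two-sided 5%, 62 per arm gives 17.04. (E.1 prints 0.90 as β; it is read here as power.) SDs of 20 and 25 are also tried.
- Shift on an unblinded call: b = 2 or 3 points, assumed.
- Mean between-arm shift = share unblinded × b. Standard error = SD × √(2/62); at SD 17.04 this is 3.06. The rejection rate comes from the noncentral t with 122 degrees of freedom.

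| Share unblinded | SD 17.04 (b = 2 / 3) | SD 20 | SD 25 |
|---|---|---|---|
| None (D.4 kept) | 5.0% | 5.0% | 5.0% |
| One quarter | 5.3% / 5.7% | 5.2% / 5.5% | 5.1% / 5.3% |
| One half | 6.2% / 7.7% | 5.9% / 7.0% | 5.6% / 6.3% |
| All | 9.9% / 16.3% | 8.6% / 13.2% | 7.3% / 10.2% |

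A simulation of the one-half row, shifting a random half of one arm's calls, gave 6.3% / 7.8%, 5.9% / 7.0% and 5.5% / 6.2%. The first row is what the plan prescribes. The last row needs D.4 to be disregarded throughout.

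**5. Would a sensitivity analysis without unblinded calls help?** Excluding 10% or 25% of calls leaves 56 or 46 per arm. Power for 10 points falls from 90% to 87% or 80% at SD 17.04, from 79% to 75% or 66% at SD 20, and from 60% to 56% or 48% at SD 25. Exclusion would also depend on which RA was free, which may go with call timing and how easily the subject was reached. That selection is not random.

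**The case for a change.** The strongest case for a change is that a promise of blinding that cannot be checked is weak protection for a subjective primary endpoint. No caller rule, call sheet, limit on data access or log of callers is given, so a reader of the results could not confirm that D.4 was kept. The protocol does more elsewhere: for the 28-day chart review, D.3.c has the statistician add the group label afterwards. With only two recruiting RAs, overlap is a realistic risk, and a caller rule would cost little.

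Part of this stands. The mechanism is unstated, and so is the party blinded under the single-blind label. The contrast with D.3.c is weaker than it looks, because that section also simply asserts that the abstractor is blinded; it does not say how someone reading the chart avoids seeing which fluid was given. The cost is also not settled. D.3.b speaks of RAs in the plural, so both could be involved with one subject, and no staffing schedule is given. Finally, the QoR-40 is answered by the patient, so the patient's own knowledge of the fluid is the more direct route to bias, and a rule about callers would leave it untouched.

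**Conclusion.** The concern does not call for a change to the plan. D.4 already requires a blinded outcome RA, and the sections on fluid handling are compatible with it. A team that follows the plan as written gets a blinded caller and an unaffected primary comparison. What is absent is operational detail: who calls whom, what the caller may see, and who is meant by single-blind. Staff can settle this sensibly in working instructions, for instance by calling each other's subjects and noting who made each call. An added analysis that drops unblinded calls would lose precision and bring its own selection, so it offers no clear gain.

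The size of any bias cannot be derived from the documents. The range of 5.1% to 7.8% for a quarter to a half of calls unblinded rests wholly on the assumed SD, share and shift, and describes departures from D.4, not the plan itself. The conclusion assumes that D.4 is treated as binding and that an uninvolved RA can be found for the call. If the conduct records showed that those who handled the fluid routinely made the calls, that would be a protocol deviation to report and weigh when interpreting the results.

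### ED disposition is listed as a baseline characteristic although it is decided after randomisation, so the imbalance rule in E.2 can call for adjustment on a possible result of the fluid

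*Combined protocol and SAP*

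**What the plan says.** D.4 separates characteristics taken at enrolment (pre-intervention QoR-40, age, gender) from a second set taken later from the chart: "Some baseline characters will be collected at the chart abstraction (ED encounter disposition [discharged from ED/admitted to hospital/admitted to ICU". ED diagnosis type is in the same later set.

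E.2 compares baseline characteristics between arms, by t-test if continuous and chi-square if categorical, and continues: "If any baseline characteristics have significant differences, those behaviors will be reported in the results section and an adjusted analysis will be performed". That analysis covers both primary and secondary variables, and its stated purpose is to assess the impact of imbalances. The primary test itself is an unadjusted t-test or Mann-Whitney test by intention to treat.

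Four other places fix the order of events:
- D.2.a: patients who "are decided to be likely to be discharged from the ED are eligible for the study".
- D.3: "Following randomization, a RA will work with the nursing staff to procure the correct IV solution and administer the solution".
- B.1: "This study proposes comparing LR and NS in a non-critically ill population, ED patients receiving fluid before discharge".
- H.1 heads its first column "Baseline (Before Intervention", in parentheses.

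**The concern.** A baseline characteristic must be fixed before treatment can act on it. Disposition is not: when the patient is randomised it is only a forecast by the provider. The plan's rationale links saline to acidosis and kidney injury and expects better recovery with lactated Ringer's, so an effect of the fluid on admission cannot be ruled out on the plan's own reasoning.

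The label matters because E.2 acts on it. A significant arm difference in admissions is the situation in which a treatment effect on disposition is most plausible, and it is also the situation in which the plan calls for adjustment. That analysis would hold constant something that may lie between fluid and recovery. It could also introduce bias if illness severity drives both admission and the score. Because E.2 reports the differing characteristic, the difference would be visible, but under the wrong name. E.2 plans no separate estimate of it as a result. D.3.c gives an outside physician 28-day treatment data by blinded group, without saying whether that includes the index disposition.

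**Working it through.** **1. Order of events.** The provider judges discharge likely (D.2.a, D.2.b); the patient is randomised; fluid is given (D.3), before discharge (B.1); disposition is then abstracted from the chart (D.4). H.1 defines baseline as before intervention. Disposition fails that definition.

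**2. Does the rule reach it?** Disposition is a categorical variable on the baseline list, so it gets a chi-square test. E.2 says any significant difference triggers adjustment. It does reach it.

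**3. The plan's own figure.** The 156 subjects in E.1 do not depend on this point. No SD is stated. With 156 × 0.8 / 2 = 62.4 completers per arm, two-sided 0.05 and 90% power, the implied SD is 10 × √(62.4/2) / (1.960 + 1.282) = 17.2. SD 17 is used below.

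**4. Size of the large-sample shift.** Among patients with outcome data:

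unadjusted − adjusted effect = (within-arm discharged-minus-admitted score gap) × (arm difference in admission)

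All inputs here are assumptions, because the documents give none: direct effect 6 points; admission costs 10 to 20 points; severity worth 0 to 8 points per SD and correlated 0.6 with the tendency to be admitted. Check at the strongest setting (20 and 8 points), 20% vs 10% admitted: 28.7 × 0.099 = 2.84.

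**5. How often the rule fires.** Three-level chi-square, 78 per arm, level 0.05 (assumed; E.2 states none for this rule), 5 to 20% of admissions going to ICU (assumed).

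| Admitted, NS vs LR | Rule fires | Shift, all admitted surveyed | Half surveyed | None |
|---|---|---|---|---|
| 20% vs 10% | 31–35% | 1.0–2.8 | 0.6–1.7 | 0 |
| 15% vs 10% | 11–12% | 0.5–1.4 | 0.3–0.8 | 0 |
| 10% vs 5% | 14–18% | 0.5–1.5 | 0.3–0.8 | 0 |
| 6% vs 3% | 8–12% | 0.3–0.9 | 0.2–0.5 | 0 |
| equal | 3–5% | 0 on average | 0 on average | 0 |

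If disposition were collapsed to two levels, the smallest admission counts of 78 that fire would include 2 vs 8 (p = 0.0498) and 4 vs 12 (p = 0.035). These assume no continuity correction. With it they do not fire (p = 0.102 and 0.065), and E.2 does not say which applies.

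**6. What happens in trials where the rule fires.** The shift in step 4 treats adjustment as always done. In fact it is done only after a significant imbalance, and that selects trials in which chance has widened the admission difference. True total effect = 6 + 20 × difference in rates, at the strongest setting with all admitted patients surveyed:

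| Rates | True total | Unadjusted mean | Adjusted mean |
|---|---|---|---|
| 20% vs 10% | 6 + 20 × 0.10 = 8.0 | about 9.7 (+1.7) | about 5.2 (−2.8) |
| 6% vs 3% | 6 + 20 × 0.03 = 6.6 | about 8.1 (+1.5) | about 5.7 (−0.9) |

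Root mean squared error around the true total effect in those trials, unadjusted against adjusted, over the range of score effects: 2.7–3.2 against 2.9–4.0 at 20% vs 10%; 2.7–3.6 against 2.7–3.2 at 15% vs 10%; 2.7–3.2 against 2.8–3.2 at 10% vs 5%; 2.8–3.2 against 2.8–3.0 at 6% vs 3%. Adjustment is clearly worse only in the first.

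**The case against.** The reach is narrow. Patients are selected as likely to go home, so admissions may be few. The fluid would have to change admission, the test would have to be significant, admitted patients would have to supply outcomes, and readers would have to give weight to a supplementary analysis. All of that stands as a limit on size.

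The survey schedule also leans against any numerical effect: "Twenty-four hours following discharge, the RAs will administer the survey again by telephone". C.1 and H.1 likewise count from ED discharge, so an admitted patient has no clearly defined survey time. If none is surveyed, disposition is constant among those analysed and adjusting for it changes nothing. The question is then one of missing data, which is separate from this point.

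Three stronger readings are tempting, and the documents do not support them. A reader might infer that the primary result is biased; it is not, because the primary test is unadjusted. A reader might take the 0.3 to 2.8 points as the error that the rule would cause; step 6 shows that where the rule fires the unadjusted estimate is itself too high, and at 6% vs 3% the adjusted one is closer to the truth. A reader might add ED diagnosis type to the charge; the documents do not say when it is fixed, so no error is claimed.

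None of this makes disposition a baseline variable or exempts it from E.2.

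**Conclusion.** The point holds as a wrong label that feeds a stated rule. Followed literally, the plan can require an adjusted analysis that conditions on a post-randomisation variable. That analysis estimates something other than the total effect of assignment, and the arm difference is presented as a chance imbalance.

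It is confined to the supplementary adjusted analysis. The primary score is affected only if admitted patients are surveyed, and there is no systematic shift unless the fluid affects disposition. The size is unknown. The figures above rest on assumed admission rates, score effects and survey completeness, and within them practical harm is small except at the largest assumed difference in admissions. Severity: minor.

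**What to change.** In D.4, take ED disposition off the baseline list and call it a post-randomisation result. In E.2, restrict the imbalance rule to variables fixed before randomisation: pre-intervention QoR-40, age and gender, plus ED diagnosis type only if it is recorded as known by then. Report disposition by arm. The unadjusted primary test and the separate covariate analysis of fluid volume and timing are outside this change.

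A relative risk with 95% CI for admission is optional and would be imprecise. With 4 (LR) vs 8 (NS) admissions of 78 per arm, SE(log RR) = √(1/4 − 1/78 + 1/8 − 1/78) = 0.591, giving RR 0.50 (0.16 to 1.59). With 8 vs 16, the SE is 0.402, giving 0.50 (0.23 to 1.10).

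The cost is wording in two sections. Disposition is already abstracted, so no new data are needed, and N stays at 156. The rule may lose ED diagnosis type as an adjustment variable.
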